8.3.2 Disease Status Evaluation using CT or MRI

The anti-tumor activity of Sym004 in combination with FOLFIRI will be assessed by the Investigator, or qualified designee, according to RECIST v1.1. Refer to [Appendix 1](#).

Patients will undergo imaging of the thorax, abdomen, and pelvis by CT or MRI as indicated, based on tumor type and prior areas of documented disease. The use of CT or MRI must be consistent per patient throughout the trial. Use of contrast is preferred but is at the discretion of the Investigator, as medically indicated.

- Screening

NOTE: A CT/MRI performed within 28 days prior to Day 1 can be used for evaluation of eligibility and as baseline scan, provided that the CT/MRI has been performed according to the protocol requirements

- End of Cycle 2 and end of every second cycle thereafter, i.e. Cycle 4, 6, 8 etc.

NOTE: End of cycle assessments may be conducted at any time during the week prior to Day 1 of the next cycle

- Suspected PD (as soon as possible)
- At least 28 days following an OR (PR, CR)
- EOT (if > 3 weeks since previous CT/MRI)
- At 1M FUP (if PD was not documented before or at EOT)

If disease progression is documented at any time, no further disease assessments will be required. Patients with documented PD will be discontinued from further treatment with Sym004/FOLFIRI so that alternative management of their malignancy may be considered.

To be assigned a status of confirmed PR or CR, changes in disease status must be confirmed by repeat studies performed no less than 28 days (4 weeks) after the criteria for response are first met. In the case of SD, follow-up measurements must have met the SD criteria at least once after trial entry at a minimal interval in general no less than 6-8 weeks.

Imaging data will be stored by the sites and will be available upon request for potential review by the Sponsor or an independent radiology reviewer.

For all imaging time points, the following will be recorded as per RECIST v1.1: Target lesions including size, location, and type (nodal/non-nodal); sum of diameters of target

lesions; any new lesions noted during trial, including size, location, and type (nodal/non-nodal); final response assessment at each visit (PD, SD, PR, CR or Not Evaluable [NE])

8.4 Pharmacokinetic Assessments (Dose-Escalation Only) [Omitted as of Amendment 3]

PK samples will be taken according to the schedules shown in Table 17 for patients in dose-escalation only. Per sampling, approximately 5 mL of blood will be obtained from patients to measure Sym004 concentration in serum.

Analysis of PK will be performed at a central laboratory. A detailed laboratory manual specifying sample collection, handling, storage and shipment will be provided to the trial sites.

In the event that a collected serum sample is inadequate for PK analysis, the analysis of PK can be done using an ADA serum sample from the same time point, if available.

Table 17 Schedule of Pharmacokinetic Assessments

		Cycle 1		Cycle 2		Cycles Thereafter	EOT	1M FUP
		D1	D15	D1	D15	D1		
Sampling Time	Window							
SOI	- 4 h	X	X	X ¹	X ^{1,2}	X ¹		
EOI	+ 10 min	X	X	X	X	X		
EOI + 1 h	+/- 15 min	X			X			
EOI + 2 h	+/- 30 min	X			X			
EOI + 4 h	+/- 30 min	X			X			
EOI + 24 h	+/- 6 h	X			X			
EOI + 48 h	+/- 12 h	X			X			
During Visit	NA						X	X

Abbreviations (in alphabetical order): D, day; EOI, End of Infusion, EOT, End of Treatment Visit; NA, Not Applicable; h, hour; min, minutes; 1M FUP, One Month Follow-up Visit; SOI, Start of Infusion

- 1) If Sym004 is paused, only one PK sample should be taken during the visit
- 2) If Sym004 is paused, the scheduled extended PK profile samples (i.e. additional timepoints EOI + 1, 2, 4, 24 and 48 hours) should be postponed until the 4th administration of Sym004 takes place

8.5 Anti-Drug Antibody Testing (Omitted as of Amendment 3)

To assess formation of ADA. All samples must be taken prior to the Sym004 infusion of that visit. Per sampling, approximately 5 mL of blood will be obtained for preparation of serum. Analysis of ADA and residual serum levels of Sym004 will be performed at a central laboratory. A detailed laboratory manual specifying sample collection, handling, storage and shipment will be provided to the trial sites. In the event that a collected serum sample is inadequate for ADA analysis, the analysis of ADA can be done using a PK serum sample from the same time point, if available.

- C1/D1

- Prior to every second cycle thereafter, i.e. Cycle 3, 5, 7 etc.
- EOT
- 1M FUP

8.6 Biomarker Tumor, Blood and Urine Sample (Omitted as of Amendment 3)

To be performed only after eligibility has been confirmed.

8.6.1 Archival Tumor Sample Collection (Omitted as of Amendment 3)

If available, archived formalin-fixed paraffin-embedded (FFPE) tumor tissue sample from a prior surgical procedure or biopsy to be submitted to a central laboratory for evaluation of RAS mutations; tissue block or cut/unstained slides are acceptable. This sample could be taken at any time from the time of diagnosis to the time of enrollment into this trial. All tumor tissue samples should be reviewed by a pathologist to confirm the presence of tumor cells before the tissue sample is sent to the central laboratory for analysis. Unused portions of paraffin blocks will be returned to the referring institution if requested. Procedures for handling and shipment will be provided.

- Screening

8.6.2 Fresh Tumor Biopsy Collection (Omitted as of Amendment 3)

To be performed only if archival FFPE tumor samples (blocks or slides) are not available for submission and only after eligibility has been confirmed.

The patient will have a tumor core biopsy of a locally recurrent or metastatic lesion. This procedure will take place after eligibility has been confirmed and prior to first Sym004 administration. The tumor biopsy must be performed with minimal morbidity to the patient by a percutaneous core biopsy needle either with or without the aid of an imaging modality chosen at the discretion of the physician performing the biopsy.

Biopsy specimens will be obtained using standard sterile surgical techniques and formalin-fixed, paraffin-embedded according to standard laboratory techniques. All tumor tissue samples should be reviewed by a pathologist to confirm the presence of tumor cells before the tissue sample is sent to the central laboratory for analysis.

- Screening (after confirmation of eligibility and only if archival tumor tissue sample is not available for central analysis)

Biomarker testing from collected tumor biopsies (archival FFPE or fresh tumor biopsy) will, if amount of tissue allows, in addition to RAS and EGFR, include biomarkers connected to EGFR signaling or escape mechanisms observed after EGFR treatment.

8.6.3 Blood and Urine Sample Collection (Omitted as of Amendment 3)

The purpose of the pharmacodynamics biomarker assessments is to develop an approach for the identification and validation of genes or proteins that may predict which patients are likely to respond to Sym004, and that may change with the possible development of acquired resistance to Sym004. Potential biomarkers of interest includes genes, gene transcripts and proteins of the Receptor Tyrosine Kinases (RTKs) and molecules of the EGFR signaling pathway.

Analysis of all samples taken for pharmacodynamics assessments will be performed at a central laboratory. A detailed laboratory manual specifying sample collection, handling, storage and shipment will be provided to the trial sites.

Patients will have blood samples taken of approximately 20 mL, for preparation of plasma, and a urine sample of approximately 100 mL.

- Screening
- End of Cycle 2 (prior to dosing or upon PD, whichever occurs first)

NOTE: End of cycle assessments may be conducted at any time during the week prior to Day 1 of the next cycle

- EOT

8.7 Handling of Biological Samples

All biological samples to be analyzed locally will be collected and handled according to institutional practices.

All biological samples to be analyzed centrally will be collected and handled according to a detailed laboratory manual.

Retention time for biologic specimens will be specified in the laboratory manual.

8.8 Follow-up Assessments

Assessments at the 1M FUP Visit include disease status and subsequent cancer therapy.

8.9 Appropriateness of Measurements

Standardized methods for assessments of efficacy and safety variables will be used.

9 ADVERSE EVENTS

9.1 Definitions of Adverse Events

9.1.1 Adverse Event

An AE is any untoward medical occurrence in a patient or a clinical investigation subject administered a pharmaceutical product and which does not necessarily have a causal relationship with this treatment. An AE can therefore be any unfavorable and unintended sign (including an abnormal laboratory finding, symptom, or disease temporally associated with the use of an IMP, whether or not considered related to the IMP.

Please Note: Progression of disease will not be captured as an AE/SAE unless the nature of the PD is different than expected (i.e. other diagnoses and/or signs/symptoms that are not typical of PD). Events associated with the actual PD will also be captured, as determined by the investigator. Additionally, AE occurring simultaneously with PD, but which may not be related to the actual PD, will also be captured.

Causality for the above-mentioned AE will be assessed appropriately as; Related to Study Drug, Not Related to Study Drug or Related to Disease Progression. In addition, any AE, regardless of causality, that also meets seriousness criteria, will be reported on an SAE Form

Events not to be considered as Adverse Events

A pre-existing condition (i.e., a disorder that is present before the AE recording period starts and is noted on the medical history/physical examination form) should not be recorded as an AE unless the condition worsens or episodes increase in frequency during the AE recording period.

Diagnostic and therapeutic non-invasive and invasive procedures, such as surgery, should not be recorded as AEs. A medical condition for which an unscheduled procedure was performed, should however be recorded if it meets the definition of an AE. For example, an acute appendicitis should be recorded as the AE and not the appendectomy.

Procedures to support the treatment regimens, such as insertion of central venous catheters etc. should not be recorded as AEs, unless the procedures result in complications.

Events such as lab results reported outside the normal range and determined to be clinically insignificant by the Investigator will not be recorded as AEs.

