9.5 Dose-Limiting Toxicities

9.5.1 Definition of Dose-Limiting Toxicities

A DLT is defined as any of the following toxicities that occur during the DLT observation period, if considered by the Investigator, and confirmed by the ISMC, to be related to Sym004 or the Sym004/FOLFIRI combination:

1. Grade 3 non-hematologic toxicity regardless of duration, with the exceptions of:
 - a. Grade 3 nausea, vomiting, diarrhea, or fatigue lasting ≤ 5 days with best supportive care
 - b. Grade 3 asymptomatic electrolyte abnormalities¹
2. Any Grade 4 non-hematologic toxicity
3. Neutropenia that is:
 - a. Grade 3 or 4, associated with fever (ANC < 1000 per mm^3 ; temperature $> 38.5^\circ\text{C}$), and requiring antibiotic therapy
 - b. Grade 4 and sustained (i.e., ANC < 500 per mm^3 , duration > 5 days)
4. Thrombocytopenia that is Grade 4 (platelets $< 25,000$ per mm^3)
5. Inability to complete Cycle 1 at the initial assigned doses of Sym004 and FOLFIRI due to \geq Grade 3 toxicity
6. Treatment delays > 2 weeks from the scheduled “next doses” due to \geq Grade 3 toxicity

¹ In addition to the scheduled ECGs (at screening and EOT), an ECG should be performed as soon as possible in the event of \geq Grade 3 hypomagnesemia, and as otherwise clinically indicated. Furthermore, in the event of QT prolongation, an ECG is to be performed prior to the next dose of Sym004. See [Section 7.2.5](#) for further details regarding procedures to address this expected AE.

[Section 12.1](#) outlines the responsibilities of the ISMC with respect to DLTs.

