10.4.1.2 Clinical Laboratory Values

Biochemistry, hematology and coagulation parameters will be presented using box plots by visits and by cohort and trial phase. In addition, individual patient biochemistry, hematology and coagulation parameters during the trial will be presented graphically using longitudinal plots. Urinalysis parameters will be summarized using descriptive statistics.

Laboratory values outside normal range by flagged and all laboratory values will be listed including CTCAE grading of abnormal values.

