12 SAFETY SURVEILLANCE SET-UP

12.1 Independent Safety Monitoring Committee

An ISMC will be established for the trial. Functions and responsibilities of the ISMC are described in an ISMC charter.

Throughout dose-escalation, the ISMC will review all reported AEs and SAEs on an ongoing basis and will decide by consensus on the following:

- Agreement with the Investigator assessment of a medical event for a patient meeting the DLT definition
- Dose-escalation
- Dose-deescalation
- Dose level expansion (i.e. another 3 patients to be included on a given dose level)
- Suspension of enrollment
- Declaration of the MTD
- Declaration of the R2PD

NOTE: All reported AEs, including those occurring after the end of the DLT observation period, will be considered for decision-making by the ISMC.

Throughout the trial, the ISMC will monitor the overall safety of the trial and provide appropriate recommendations to the Sponsor regarding trial continuation, protocol modifications or trial suspension.

The conclusion of the ISMC meeting will be provided verbally to the Sponsor immediately after each meeting followed by signed written minutes within a few days.

Any safety related ISMC recommendation that may result in protocol changes will be reported to the HAs and IECs/IRBs. A letter of trial continuation after each ISMC meeting will be supplied to IECs/IRBs only if required.

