For Grade ≥ 3 nonhematologic toxicities not described above, withhold treatment with FOLFIRI and monitor toxicity at least weekly. If toxicity resolves to Grade ≤ 1 within 2 weeks, treatment may be resumed with 5-FU and irinotecan at 1 dose level lower. For Grade 3 toxicities associated primarily with laboratory abnormalities only (for example, elevation of ALT, AST, hyperlipasemia, hyperamylasemia, hypophosphatemia without clinical or other evidence of pancreatitis or other hepatic dysfunction), study treatment may continue without interruption at the discretion of the investigator.

Neurocerebellar Toxicity

In the event of neurocerebellar toxicity, treatment with 5-FU should be discontinued.

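### Section 9.1.1 lets a laboratory value that meets a dose-limiting toxicity criterion in 9.5.1 go unrecorded as an adverse event, so it can be filtered out before the safety committee confirms it

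*Protocol*

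**What the plan says.** Protocol 9.1.1 first gives the general definition: "An AE can therefore be any unfavorable and unintended sign (including an abnormal laboratory finding" and so on. It then lists what is not an adverse event, ending with: "Events such as lab results reported outside the normal range and determined to be clinically insignificant by the Investigator will not be recorded as AEs". No CTCAE grade limits this exclusion, and nothing excepts values that meet a DLT criterion.

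Protocol 9.5.1 defines DLTs in the observation period, subject to the Investigator's judgement of relatedness and confirmation by the ISMC. Criterion 1 is "Grade 3 non-hematologic toxicity regardless of duration, with the exceptions of" two items, of which the only laboratory one is "Grade 3 asymptomatic electrolyte abnormalities". Criterion 2 is "Any Grade 4 non-hematologic toxicity". Hematologic values have their own thresholds: neutropenia counts with fever and antibiotics, or at Grade 4 for more than 5 days, and thrombocytopenia counts at Grade 4.

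Protocol 8.2.3 describes the DLT evaluation in terms of adverse events that meet DLT criteria. Under 12.1, during dose escalation, "the ISMC will review all reported AEs and SAEs on an ongoing basis", and it decides whether it agrees with the Investigator's DLT assessment.

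Protocol 10.4.1.2 provides that "all laboratory values will be listed including CTCAE grading of abnormal values".

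**The concern.** The two sections apply different tests to the same value. Section 9.5.1 asks for grade, relatedness and timing. Section 9.1.1 adds a further test, clinical significance in the Investigator's opinion, and applies it when the event is recorded. Nothing says which section prevails.

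The affected values are foreseeable. AST, ALT, bilirubin, amylase, lipase and CK are in the biochemistry panel (8.2.9.2), drawn on Days 1, 8, 15 and 22 of Cycle 1. An isolated Grade 3 rise in one of these is a result an Investigator might well call insignificant. The summary of Amendment 2 (21.2) shows how the mismatch arose: that amendment added the exclusion to 9.1.1 and took the Investigator's view of clinical relevance out of the electrolyte exception in 9.5.1.

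At stake are the escalation decision in a 3 + 3 design, where one patient can be decisive, and the completeness of the DLT table in 10.3.1. The study report could list a graded Cycle 1 value that meets 9.5.1 and yet has no entry in the DLT table.

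**Working it through.** The plan states no figure on this point, so there is none to reproduce. The check is a comparison of the texts, followed by the effect of one missed event.

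**1. Which laboratory values qualify under 9.5.1, if judged related**

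| Cycle 1 value | DLT by grade? |
|---|---|
| Grade 3 non-electrolyte chemistry (e.g. ALT, AST, lipase, amylase, CK) | Yes, criterion 1, any duration |
| Grade 3 electrolyte, asymptomatic | No, exempt |
| Grade 4 non-hematologic, electrolytes included | Yes, criterion 2 |
| Isolated Grade 3 neutropenia or thrombocytopenia | No |

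**2. Whether 9.1.1 can remove a qualifying value.** Yes. Its only test is the Investigator's judgement of significance, so it reaches the first and third rows.

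**3. Whether another route catches it**

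- *Serious adverse event reporting (9.2.3).* A Grade 4 laboratory abnormality is reported as serious only if it meets a seriousness criterion, so this is no general backstop.
- *24-hour DLT report to the Sponsor (9.5.3).* It does not depend on an adverse event entry, but it starts only when a DLT is presumed.
- *Scheduled DLT evaluation (Table 2, 8.2.3).* It is a separate assessment, but 8.2.3 frames it as adverse events meeting DLT criteria.
- *ISMC review of all relevant safety data (10.5).* This is broader than 12.1, but it does not say that unrecorded laboratory values are included.
- *Medical Monitor (12.2).* The role evaluates abnormal laboratory values and updates the ISMC on trial status, but is not required to forward qualifying values.

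**4. Effect of one missed DLT under 7.1.4.3**

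- True 1 of 3, counted 0 of 3: escalation may proceed instead of three more patients being added.
- True 2 of 6, counted 1 of 6: the dose is taken as not exceeding the MTD, when the rule says it does.

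A missed event can only lower the count, so the error has one direction.

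**5. How sensitive the rule is (illustration only).** Let p be the true DLT risk per patient, and q the share of DLT patients whose only DLT is an unrecorded laboratory value. Both are assumptions; the protocol gives neither. With r = p(1 − q), the chance of escalating is

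(1 − r)^3 + 3r(1 − r)^5.

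For p = 0.3 and q = 0: 0.343 + 0.9 × 0.168 = 0.49. For p = 0.3 and q = 0.25, r = 0.225: 0.465 + 0.675 × 0.280 = 0.65.

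| p | q = 0 | q = 0.10 | q = 0.25 | q = 0.50 |
|---|---|---|---|---|
| 0.2 | 0.71 | 0.75 | 0.81 | 0.91 |
| 0.3 | 0.49 | 0.56 | 0.65 | 0.81 |
| 0.4 | 0.31 | 0.38 | 0.49 | 0.71 |
| 0.5 | 0.17 | 0.23 | 0.35 | 0.60 |

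The q = 0 column is the rule as written. The other columns show direction and sensitivity; they do not estimate what happened in this trial.

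**The case against.** The strongest reply is that the safeguards in step 3 overlap. A site has several scheduled DLT assessments in Cycle 1, the Sponsor's Medical Monitor looks at laboratory values, the ISMC may ask for anything relevant, and its charter, which is not at hand, may require laboratory data. The stagger in 7.1.4.3 also exists so that the first patient's laboratory results are reviewed. This stands in part: it makes a missed DLT less likely. None of the text available, however, requires a qualifying value that the Investigator has dismissed to be recorded or forwarded.

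A second reply is that a value judged insignificant is not a toxicity at all, so 9.5.1 never applies. The protocol's own wording is against this. An exemption for asymptomatic Grade 3 electrolytes would be needless if laboratory-only findings were not toxicities.

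Four stronger readings are tempting and are not supported:

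- *That every Grade 3 or higher laboratory abnormality is a DLT.* Asymptomatic Grade 3 electrolytes are exempt, and electrolyte imbalance is the laboratory toxicity listed as expected with Sym004 (9.1.3). Isolated Grade 3 cytopenias do not qualify by grade.
- *That open-label judgement is itself the fault.* Relatedness is already an Investigator judgement under 9.5.1, but the ISMC confirms it. The problem is the additional filter that acts before the ISMC is involved.
- *That Appendix 2 contradicts 9.5.1.* For Grade 3 laboratory-only events it says that "study treatment may continue without interruption at the discretion of the investigator". That governs treatment. Under 6.3.1 a DLT requires withdrawal only if the Investigator considers that it does, so an event can be a DLT while treatment continues.
- *That a large share of cohorts is affected.* If 2%, 5% or 10% of patients are assumed to have such a value, 1 − (1 − p)^6 gives 11%, 26% or 47% for at least one in six patients. Nothing in the protocol anchors those rates, and the result is the chance that a value occurs. A wrong decision also needs the value to be dismissed, missed by the other routes and decisive for the count.

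**Conclusion.** Sections 9.1.1 and 9.5.1 are not reconciled. For related Grade 3 non-electrolyte chemistry and any related Grade 4 non-hematologic value, following 9.1.1 as written can keep a qualifying event out of the record that 12.1 names for ISMC review. Sections 9.5.3, 10.5 and 12.2 lower the risk without closing the gap. A single missed event can change a cohort decision, always toward a higher dose. How often this would happen cannot be said, because the protocol gives no rate.

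The practical weight is now limited. Amendment 3 stopped enrollment (5.5) and declared the objectives no longer applicable (4.1), so no further escalation decision depends on the wording. What remains is whether the DLT listing and table in 10.3.1 are complete. The conclusion rests on the protocol alone; the ISMC charter could narrow the gap further.

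**What to change.** Add one sentence to 9.1.1: any laboratory value in Cycle 1 of dose escalation that meets a grade criterion in 9.5.1 is recorded as an adverse event with its relatedness and sent to the ISMC, whatever its judged clinical significance. Worded this way, the rule leaves the DLT definition unchanged and prescribes nothing about treatment.

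Since enrollment has stopped, also compare the Cycle 1 graded laboratory listing (10.4.1.2) with 9.5.1 before the DLT table is finalised. For any qualifying value without an adverse event record, obtain the relatedness assessment and the ISMC's view; the listing alone does not show relatedness.

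The cost is a few more adverse event records and one reconciliation step. The values are already collected on Days 1, 8, 15 and 22 of Cycle 1. No sample size changes, and Appendix 2 needs no change on this account.
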